## 2 Study Objectives

## 2.1 Primary Objective(s)

The primary objective of this study is to observe the rate of recovery of ventricular function (EF>35%) between 90 and 180 days in newly diagnosed HF with reduced EF patients who were prescribed the WCD while being initiated on their HF medications. This will be measured from EF closest to before hospital discharge, then at 90, 180 and 360-days after WCD start, regardless of continued WCD use, prior EF improvement, or ICD implantation. While approximately one-third of the patients will likely experience EF recovery in the first 90 days, we hypothesize that an additional 5-10% of patients will experience EF improvement between 90 and 180 days as GDMT is achieved. This would be considered clinically significant in terms of the potentially avoided ICD implantations. Outcomes will be tracked and reported for three pre-specified groups based on assessment of SCD risk at 90 days of WCD use:

- 1) Patient improved (EF >35%), SCD risk deemed to be negligible. These patients are expected to end WCD use and not receive an ICD.
- 2) Patient improved EF from start of WCD use (a positive change of at least 5 percentage points in EF), or has a borderline EF of 30-35%, but still has continued SCD risk (EF ≤ 35%). These patients are expected to continue to use the WCD for an additional 3 months.
- 3) Patient not improved from start of WCD use (no change or worsening of EF), EF<30% and has continued high SCD risk. Those on GDMT are expected to be evaluated for an ICD. Those not yet on GDMT may continue the WCD for an additional 90 days.

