#### 3.2.2 LVEF recovery

To support our primary hypothesis that an additional 5% of patients will experience EF improvement between 90-180 days, EF measurement for all patients at 90 (±14), 180 (±14) and 360 (±14)-days after WCD start will be requested and recorded. For this study, EF>35% will be considered as EF improved.

- 3.2.2.1 Echocardiographic assessment of LVEF is most common. Nevertheless, other imaging modalities (MUGA, MRI) may be used to document LVEF at day 0. Although there are likely to be differences in EF assessment among enrolling sites and practices, these differences are not expected to affect the outcome of the trial. At a minimum, we will request a 2-D, M-mode echo at the scheduled time-points.
- 3.2.2.2 Echocardiogram core lab verification. EF is commonly estimated by echocardiogram. Several studies have shown EF measurement to have a wide range of variability that can be observer dependent. Study echocardiograms will be sent to a core lab for a uniform determination of the EF. The core lab determinations will be used to verify local estimates of EF and may be used in secondary analyses of the study data

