## 7.2 Managing WCD Therapy

Since this is an observational, unblinded study, WCD therapy will be handled following normal commercial procedures. However, sites will be notified if a patient receives a shock, and ECG recordings of the event will be sent for the completion of the SCA/Defibrillation event CRF. Evaluation and treatment of patients receiving a shock will be determined by the treating physician.

Treatment events will be initially determined to be appropriate or inappropriate by each site's principal investigator. All shocked events and terminal ECG recordings will be adjudicated by a committee independent of the sponsor. Information regarding the treatment event will be captured in the SCA/Defibrillation event CRF.

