#### 8.1.1 Statistical design used for sample size calculation

This dataset will be used evaluate among all patients, if more than 5% of them will experience EF improvement between 90 and 180 days ( $n_5/n > 5\%$ ).

To calculate the number of samples (n), we first calculated  $n_4$ , then calculated n based on the following formula:

$$n = \frac{n_4}{P_{followup2}} * \frac{1}{p_{wcd}} * \frac{1}{P_{followup1}}$$

where  $p_{wcd}$  is the percentage of patients who will wear WCD beyond 90 days ( $n_1/(n_1+n_2+n_3)$ ,  $p_{followup1}$  and  $p_{followup2}$  are the percentage of patients with proper follow up from 0 to 90 days and from 90 days to 180 days respectively, both of the them equals to 0.85 (1-0.15=0.85).

To calculate sample size for  $n_4$ , we performed superiority test. The statistical hypothesis to be tested is:

[figure not shown]
$$H0: P \le P_0 + \delta \text{ vs } H1: P > P_0 + \delta$$

The sample size of superiority test is calculated as the following formula:

$$n_4 = p(1-p) \left( \frac{Z_{1-\alpha} + Z_{1-\beta}}{p - p_0 - \delta} \right)^2$$

where p is the actual proportion of patients who will have EF improvement ( $n_5/n_4$ ).  $p_0$  is the baseline proportion, and specified as 0.001 (close to 0).  $\delta$  is the test margin, since the hypothesis is that more than 5% of them will experience EF improvement between 90 and 180 days ( $n_5/n > 5\%$ ),  $\delta$  depends on  $p_{wcd}$  as  $\delta = 0.05/P_{wcd}$ . We also specify  $\alpha$  as 0.05,  $\beta$  as 0.1

As shown in figure above, sample size (n) depends both on p, the actual proportion of patients who will have EF improvement (p=n5/n4) and  $p_{wcd}$ , the percentage of patients who will wear WCD beyond 90 days ( $p_{wcd} = n_1/(n_1+n_2+n_3)$ ).In this study, we specify  $\alpha$  as 0.05,  $\beta$  as 0.1. We predict that about 1/3 patients will have continued WCD wear from 90 to 180 days; and actual proportion of WCD patients at 90 days to have further EF improvement is 23%. In this case, we plan to prescribe WCD to 868 patients (initial registry sample size), in order to have approximately 738 patients eligible for the study at day 90. If mid-study analysis shows continued WCD use to be far out of 1/3, then sample size will be re-adjusted as necessary.

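### The plan does not name the EF reading behind its EF>35% outcome, limits the core-lab EF to verification and optional secondary use, and sizes the study on a one-way count that reading error inflates

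*Combined protocol and SAP*

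**What the plan says.** Section 3.2.2 sets a hard cut-off: "EF>35% will be considered as EF improved". Item 3.2.2.1 accepts that EF assessment will differ among sites and practices, and adds that "these differences are not expected to affect the outcome of the trial". Item 3.2.2.2 then says: "Several studies have shown EF measurement to have a wide range of variability that can be observer dependent". It continues: "Study echocardiograms will be sent to a core lab for a uniform determination of the EF". The use of that reading is limited: "The core lab determinations will be used to verify local estimates of EF and may be used in secondary analyses of the study data". Section 2.4 repeats the limit. No section names the reading that defines the primary outcome, gives a rule for discordant local and core-lab values, or plans a sensitivity analysis on the source of EF.

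Section 8.1.1 states the quantity to be tested, "if more than 5% of them will experience EF improvement between 90 and 180 days", written as n5/n > 5%. Section 8.3.1 plans descriptive comparisons, including mean EF and the percentage above 35% at 90 and at 180 days.

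On blinding, section 3.1.2 speaks only of WCD device records and section 6.6 is marked not applicable. Section 7.2 opens with "Since this is an observational, unblinded study", but its subject is WCD therapy. Nothing is said about what echo readers know, locally or at the core lab.

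**The concern.** Patients can add to n5 only if they read at or below 35% at day 90. Some of them are there because that reading was low by error. At day 180 they can read above 35% with no change in the heart, and a one-way count records this as recovery. The larger the within-patient reading error, the larger the spurious share. The bar is only 5% of patients, so moderate error matters.

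The plan expects many of the patients who continue the WCD to lie close to the cut. Group 2 in section 2.1, expected to wear it for three more months, includes those with EF 30 to 35%.

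A uniform reading is already being obtained, and the plan does not commit to using it for the outcome it would most help. At stake is whether a result above 5% could be read as late recovery under medical therapy.

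**Working it through.** **The plan's own figures (section 8.1.1).** With p_wcd = 1/3, the margin is δ = 0.05/(1/3) = 0.15. The bar for the proportion converting among WCD continuers is 0.001 + 0.15 = 0.151. The assumed proportion is 0.23, so the planned n5/n is 0.23 × 1/3 = 7.67%. This counts continuers only. The printed formula gives n4 = 0.23 × 0.77 × [(1.645 + 1.282)/0.079]² ≈ 243. Carrying that through both 0.85 follow-up factors gives 243/0.85 × 3/0.85 ≈ 1,009, not the stated 868. That is a separate matter, and nothing below depends on it.

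**Inputs for the noise check.**
- Cut-off 35% (section 3.2.2).
- One-third above 35% at day 90. Section 2.1: "While approximately one-third of the patients will likely experience EF recovery in the first 90 days".
- True EF SD s: not in the documents; assumed 8 to 12 points.
- Reading SD e (error between two readings of the same patient): not in the documents; assumed 2, 3 and 5 points.
- No true change from day 90 to day 180; errors normal and independent.

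**Formula.** Each reading has SD √(s² + e²), and the two readings correlate at ρ = s²/(s² + e²). The standardised cut is z = Φ⁻¹(2/3) = 0.431. The share of all patients at or below 35% at day 90 and above it at day 180 is 2/3 − Φ₂(z, z; ρ), where Φ₂ is the bivariate normal distribution function.

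Example, s = 9 and e = 3: SD = √90 = 9.49, ρ = 81/90 = 0.90, Φ₂ = 0.6014, share = 0.6667 − 0.6014 = 6.5%.

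**Upward crossing by noise alone, % of all patients**

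| Reading SD | s = 8 | s = 9 | s = 10 | s = 12 |
|---|---|---|---|---|
| 2 | 5.0 | 4.5 | 4.0 | 3.4 |
| 3 | 7.3 | 6.5 | 5.9 | 5.0 |
| 5 | 11.1 | 10.1 | 9.3 | 8.0 |

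The share reaches 5% at a reading SD of about 2.0, 2.25, 2.5 and 3.0 points for s = 8, 9, 10 and 12.

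**If only WCD continuers can count.** Two-thirds of patients are at or below 35% at day 90 and the plan expects one-third of all patients to continue, so about half of that group continues. At s = 9, as % of all patients:

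| Reading SD | Random half continues | Only those reading 30-35% count | Half nearest 35% continues |
|---|---|---|---|
| 2 | 2.2 | 4.3 | 4.5 |
| 3 | 3.3 | 5.5 | 6.3 |
| 5 | 5.1 | 6.2 | 8.7 |

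Among patients reading 30 to 35% at day 90, noise alone moves 20%, 27% and 33% above the cut at reading SD 2, 3 and 5. The plan assumes 23% conversion among continuers.

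**Net comparison (section 8.3.1).** In the same model the share above 35% is one-third at both visits. Downward crossings equal upward crossings and the net change is zero. Only a systematic shift of d points at day 180 alters it: net change = 1 − Φ(z − d/√(s² + e²)) − 1/3. For d = 1 point this is 2.8 to 4.5 percentage points over s = 8 to 12 and e = 2 to 5.

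**What a better reading buys.** At s = 9, cutting the reading SD from 5 to 3 lowers the spurious share of all patients from 10.1% to 6.5%; cutting it to 2 lowers it to 4.5%.

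**The case against.** A reader might infer that the outcome is read by local staff who know the device, the visit and the earlier EF. The documents do not say this. Local reading is an inference from the core lab's limited role, and lack of blinding is an inference from silence. What stands is that neither is specified.

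A reader might also infer that the 5% threshold will be met with no recovery at all. That is too strong. It does not apply to the net 90 versus 180 day comparison, where symmetric error cancels. Section 8.3.1 also looks at individual EF patterns, including a peak followed by decline, so downward movement is not ignored. In the one-way count, the bar is not passed at a reading SD below about 2 points, nor at 3 points if continuers are a random half of those at or below 35%.

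Setting the all-patient 10.1% beside the planned 7.67% would mix two populations, since the latter counts continuers only. Which count applies is itself open: section 2.1 measures EF regardless of continued WCD use, while the sample-size formula builds n5 from continuers.

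The sentence containing "these differences are not expected to affect the outcome of the trial" is about differences among sites. A constant site offset does not make a patient cross between visits, so the calculation does not refute that sentence. It remains unsupported by any figure and leaves within-patient error unaddressed.

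Finally, local EF is defensible in an observational study whose stated interest is ICD implantations avoided, because clinicians act on it. That is a reason to keep and report it, but not to leave the primary source unnamed.

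**Conclusion.** The concern holds as a gap in specification with a measurable consequence for one quantity. The plan names neither the primary EF reading nor any blinding of readers, and it gives the uniform reading a minor role. The one-way count n5/n, the only quantity with a stated hypothesis test, is inflated by reading error: with no true change, about 3.4-5.0% of all patients at a reading SD of 2 points, 5.0-7.3% at 3 and 8.0-11.1% at 5. The figures are about half that if a random half of those at or below 35% continue the WCD, and higher than half if continuers sit near the cut. The net comparison is biased only by a systematic shift in readings, and the documents give no evidence of one.

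All of this rests on an assumed EF spread and reading error, normal and independent errors, and the plan's one-third above 35% at day 90. The point is a cheap improvement. It does not show that the study's conclusion would be wrong.

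**What to change.** - Name the core-lab EF as the primary measurement of EF>35% at 90, 180 and 360 days, read blind to local EF, device and visit order. State a fallback for unreadable studies.
- Keep local EF as the sensitivity analysis and as the description of what drove care.
- Beside n5/n, report downward crossings and the net change in the percentage above 35%. State whether n5 counts all patients or WCD continuers only.
- Remove or qualify the sentence in 3.2.2.1, repeated in 6.2.1.3.1, that differences in EF assessment will not affect the outcome.

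The cost is mainly wording in the statistical plan and a reading instruction to the core lab, since the study echoes already go there. The downsides are that some echoes may be unreadable, core-lab EF may differ from the EF clinicians acted on, and core-lab reading reduces the noise without removing it. That last limit is why the downward and net figures are needed as well.

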## 3.3 Secondary Study Endpoints

The secondary endpoints are observational and include documentation of any SCA/SCDs, including any treatments by the WCD or ICD, any untreated sustained ventricular arrhythmias that are recorded by the WCD, and the mortality following discharge in HF patients. We will also collect economic and healthcare utilization data on all patients.

3.3.1 SCA/SCD, Sustained Ventricular Arrhythmias, and Mortality

3.3.1.1 "Sudden Cardiac Death" will be defined as an unexpected, non-traumatic, non-self-inflicted fatality in otherwise stable subjects who die within one hour of the onset of the terminal symptoms. Subjects dying more than one hour after a sudden cardiac arrest (SCA) from a ventricular arrhythmia will be designed as non-sudden death due to ventricular arrhythmia. For unwitnessed deaths participants will meet the definition of sudden cardiac death if they are found dead within 24 hours of being well, assuming there is no evidence of another cause of death during that time period. Autopsy results may be used when available.

For the mortality analysis, all deaths will be classified by the site investigator as cardiac or non-cardiac, and sudden or non-sudden.

- 3.3.1.2 "Appropriate detection" will be defined as a device alarm/detection during a ventricular tachyarrhythmia.
- 3.3.1.3 "Sustained ventricular arrhythmia" will be defined as any WCD-recorded appropriate detection with ≥ 30 seconds of uninterrupted VT/VF.
- 3.3.1.4 "Appropriate treatment" will be defined as a therapy shock or anti-tachycardia pacing (ATP) given during a ventricular tachyarrhythmia.
- 3.3.1.5 "Inappropriate treatment" will be defined as a therapy shock and/or ATP (for ICD recipients) delivered in the absence of an appropriate detection.
- 3.3.1.6 "Other treatment" will be defined as a therapy shock delivered during an appropriate detection but on a section of the recording not showing a ventricular arrhythmia.
- 3.3.2 Effectiveness of the wearable defibrillator in treating ventricular arrhythmias

Clinical outcomes and device data from any defibrillation or cardiac event will be reviewed for success as defined by appropriate detection and defibrillation, conversion out of the detected ventricular arrhythmia, and consciousness when medically evaluated after treatment.

- 3.3.3 Incidence of other WCD recorded arrhythmias, such as asystole and supra-ventricular arrhythmias.
- 3.3.4 Economic and healthcare utilization data on all patients

Information (days, reasons) on any hospitalizations, emergency room visits, observation stays, urgent care visits, other physician office visits, and stays at skilled nursing facilities.

## 3.4 Safety Endpoints

The safety objectives will be to compare complications from extended use of the WCD with those of the ICD during the study timeframe.

- 3.4.1 Complication data from ICDs for those who receive an ICD, including inappropriate interventions or other ICD-related complications that may lead to hospitalization or death.
- 3.4.2 Complication data from WCDs, including inappropriate shocks or other WCD-related complications that may lead to hospitalization or death.

## 4 Study Subject

#### 4.1 Inclusion Criteria

The population for this study will be patients who had an ejection fraction (EF)  $\leq$  35% following hospitalization for newly diagnosed HF, and who have already been using a WCD for 90 days. Prior to 90 days, eligible patients will be enrolled into a registry. Registry patients will be enrolled during the first 30 days of WCD use.

All of the following must be true for enrollment into the registry (day 0 – 90 of WCD use):

- 4.1.1 Patients (≥18 years old) who were prescribed the WCD ≤ 10 days post-discharge after hospitalization for a primary reason of newly diagnosed HF with reduced EF (≤30 days since first HF hospitalization), with ischemic or nonischemic cardiomyopathy, and have used the WCD for no more than 30 days.
- 4.1.2 Patients who had an EF  $\leq$  35% during index hospitalization.

All of the following must be true for enrollment into the study (day  $90 \pm 14$ ):

- 4.1.3 Patients (≥18 years old) who were prescribed the WCD ≤ 10 days post-discharge after hospitalization for a primary reason of newly diagnosed HF with reduced EF (≤30 days since first HF hospitalization), with ischemic or nonischemic cardiomyopathy, and either 1) have already used a WCD for 90 ± 14 days or 2) were enrolled in the registry after 01-March-2019 and received an ICD prior to 90 days of WCD use.
- 4.1.4 Patients who had an EF  $\leq$  35% during index hospitalization. Of note, EF at 90  $\pm$  14 days post-hospitalization does not need to be low to be included in the study.

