## 6 Study Procedures

## 6.1 Subject Recruitment and Screening

### 6.1.1 Subject screening for WCD registry and study

Patients will initially be screened from the prescribed WCD patients and enrolled into the prestudy registry. At 90  $\pm$  14 of WCD use, study subjects will be identified and screened from the clinical site's pre-study registry participants. The sponsor may also assist in the screening process by maintaining a current list of WCD prescribed patients to be screened for the registry by each site. Registry participation is complete when the patient enters the HF Opt study, or ends WCD use.

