#### 6.3 Unscheduled Visits

Unscheduled visits for registry or study patients may include:

collected.

6.3.1 Resuscitation from SCA event, death, inappropriate shock, and unanticipated end of WCD use or study completion (immediately following notification of occurrence)

6.3.1.1	In the event of a WCD recording that indicates shock, sustained VT/VF >30
	seconds with no shock, or asystole (<10 BPM), sites will be notified from
	ZOLL of the occurrence, and ECG strips will be sent.

- 6.3.1.2 Clinical data will be collected, including any additional EF measurements that were taken at the end of WCD use.
- 6.3.1.3 Device information, adverse events, and cardiac event information will be collected.
- 6.3.1.4 At the end of the study or WCD device use, the reason for discontinuing will be recorded.

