## 11 Administrative Responsibilities

## 11.1 Sponsor

ZOLL, the Sponsor, is responsible for study administration as well as providing devices and related materials for the study. The Sponsor will select appropriate investigators, assure collection of investigator agreements, assure IRB approval of the protocol, and monitor informed consent records.

The sponsor may also assist in the screening process by maintaining a current list of eligible patients to be screened by each site (i.e., those patients who are still active WCD users at day 90  $\pm$  14).

The Sponsor will designate appropriately trained and qualified individuals to monitor the investigation. These individuals will verify the adherence to procedures specified in the protocol, and verify maintenance of required subject and data records.

The Sponsor will provide trained and qualified individuals to fit subjects with the WCD and to provide training on the use of the WCD.

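### The day-90 entry rule shuts out patients who recovered and stopped the WCD early, so with study enrollees as denominator 90-day recovery is likely understated and the 90–180 day share likely inflated

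*Combined protocol and SAP*

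**What the plan says.** **Entry.** Section 4.1.3 gives two routes into the study. Under route 1 patients "have already used a WCD for 90 ± 14 days", that is, 76 to 104 days. Under route 2 they "were enrolled in the registry after 01-March-2019 and received an ICD prior to 90 days of WCD use". Section 4.1.4 adds that the day-90 EF "does not need to be low to be included in the study", but the patient must still meet route 1 or route 2.

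**Registry.** Section 6.1.1: "Registry participation is complete when the patient enters the HF Opt study, or ends WCD use". Table 1 (section 6.5) lists registry echo data at the initial visit only. For end of WCD use, section 6.3.1.2 says: "Clinical data will be collected, including any additional EF measurements that were taken at the end of WCD use", so an EF is captured only if one was done. Section 11.1 describes the sponsor's day-90 screening list as "those patients who are still active WCD users at day 90". Section 3.1 says the registry supplies 90-day outcomes, but for patients likely to be eligible at day 90, or eligible and refusing.

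**Objective and analysis.** Section 2.1 wants EF at 90, 180 and 360 days "regardless of continued WCD use, prior EF improvement, or ICD implantation". It expects about one-third of patients to recover in the first 90 days and a further 5–10% between 90 and 180 days. Section 8.1.1 puts the hypothesis this way: "This dataset will be used evaluate among all patients, if more than 5% of them will experience EF improvement between 90 and 180 days". Section 8.3.1 compares the percentages above 35% at 90 and 180 days without naming a denominator.

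**The concern.** A patient whose EF rose above 35% at, say, day 60 and who then stopped the WCD leaves the registry and cannot enter the study. A patient who stopped on the same day because of an ICD can enter, if registered after 01-March-2019. Entry therefore depends partly on the outcome being studied, and this conflicts with the aim in section 2.1.

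If the percentages are computed on study enrollees, early recoverers are missing from the 90-day numerator and from both denominators. The result would then be quoted for all newly diagnosed patients given a WCD, and set against a 5% threshold, although it describes a selected subset. Section 8.6.3.2 rules out replacing missing data, so no later step corrects this.

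**Working it through.** **The plan's own figures.** The planning share is 0.23 × 1/3 = 7.67%, and 868 × 0.85 = 738 reproduces. The printed formula with p = 0.23, p0 = 0.001, p_wcd = 1/3, one-sided α = 0.05 and β = 0.1 gives n4 = 243.0. Then n = 243.0/0.85/(1/3)/0.85 = 1009, not 868. Leaving out the second follow-up factor gives 858. That discrepancy is a separate matter, and nothing below depends on it.

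**Which denominator?** In the formula of section 8.1.1, n is the initial registry size. But the margin δ = 0.05/p_wcd, with p_wcd = n1/(n1+n2+n3), ties the 5% to the set divided up at day 90. The figure in that section was not available in the text used here, so this reading rests on the wording and formulas alone.

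**Bias if enrollees are the denominator.** Inputs from section 2.1: R = 1/3 recovered by day 90, and S = 5%, the lower end of its range, recovering between 90 and 180 days. Two quantities are not in the documents and are assumed over a range:

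- f: share of the cohort that recovered and stopped before about day 76.
- g: share that stopped early without recovery and did not enter. These patients are taken to recover later at the same rate as other non-recovered patients, u = S/(1 − R) = 0.05/(2/3) = 7.5%.

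Then:

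- enrolled 90-day recovery = (R − f)/(1 − f − g)
- enrolled 90–180 share = (S − u·g)/(1 − f − g)

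| f | g | 90-day recovery | 90–180 share |
|---|---|---|---|
| 0 | 0 | 33.3% | 5.00% |
| 5% | 0 | 29.8% | 5.26% |
| 10% | 0 | 25.9% | 5.56% |
| 15% | 0 | 21.6% | 5.88% |
| 20% | 0 | 16.7% | 6.25% |
| 10% | 10% | 29.2% | 5.31% |
| 10% | 20% | 33.3% | 5.00% |
| 10% | 30% | 38.9% | 4.58% |

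**Direction.** Both figures move as described only when f/(f + g) > R, so recovered patients must be more than about one-third of those shut out.

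**Effect at the threshold.** With f = 10% and g = 0, a true share of 4.5% reads as 0.045/0.90 = 5.0%. If δ is recomputed from enrollees, p_wcd goes from 0.333 to 0.333/0.90 = 0.370 and δ from 0.150 to 0.135. Suppose exactly 5% of the full cohort recovers late, so that n5/n4 = 0.15, and n4 = 243. The standard error is √(0.15 × 0.85/243) = 0.0229. The one-sided error is 1 − Φ(1.645 − 0.015/0.0229) = 0.16, or 0.15 with p0 = 0.001, against about 0.05 without selection.

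**What does not move.** Recovery among patients with EF ≤35% at day 90 is 7.5% in every row. It does not depend on f at all, and it does not depend on g under the equal-rate assumption. The ratio n5/n4 does not depend on f either.

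**The case against.** The strongest defence is that the population is declared: the study summary and section 4.1 describe patients who have already worn a WCD for about 90 days. No echo is scheduled between the initial visit and day 90. Section 2.1 places the end of WCD use for improved patients after the 90-day assessment, and a recovered patient still wearing the device at day 76 can enter. So f may be small. That stands as a limit on size. It does not remove the conflict with section 2.1 or supply a denominator. If the registry n is the denominator, this inflation does not arise.

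A reader might also draw stronger conclusions that the documents do not support:

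- *The later share is certainly inflated.* Patients who stop early without recovery are shut out too and pull the other way. So were early ICD recipients registered up to 01-March-2019.
- *Route 2 itself inflates the share.* In the planning model n5 comes from n4, the WCD continuers. Early ICD recipients add to the denominator, lower p_wcd and raise δ, so they tend to lower n5/n.
- *Selection alone carries the planning value over 5%.* Rescaling 7.67% by (1 − f) gives 7.67% × 2/3 = 5.1% even if every expected early recoverer were lost, still above 5%. The rescaling may also double count: the formula removes only 15% before day 90, so the one-third wearing on may already be a share of all followed starters.
- *The caps show heavy early recovery.* 1 − 600/1400 = 57% compares two upper limits, and the gap also covers refusals, exclusions, losses and deaths.
- *Patients registered before and after the date cannot be compared.* Only the early-ICD subset differs.

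**Conclusion.** The entry rule selects in part on recovery status, it conflicts with section 2.1, and the denominator is not defined. If study enrollees are used, 90-day recovery is likely understated and the all-patient 90–180 share likely inflated, on condition that recovered patients exceed about one-third of those shut out. For assumed f of 5–20% with no other early exits, 90-day recovery falls from 33.3% to between 29.8% and 16.7%, and a 5% share reads as 5.3% to 6.25%. The documents give neither f nor g, so direction and size are conditional. The point should be settled before analysis, because otherwise the denominator can be chosen after the data are seen.

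**What to change.** In sections 8.1.1 and 8.3.1:

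1. State the 5% hypothesis for registry patients from WCD start.
2. Count patients who ended WCD use early with a documented end-of-use EF above 35% as recovered before day 90.
3. Tabulate early exits by reason and by EF, where known.
4. For early enders with no later EF, show bounds: none, then all, recovering between 90 and 180 days. Add a sentence to section 8.6.3.2 permitting this.
5. Report the 90–180 rate among patients with EF ≤35% at day 90 alongside the all-patient share.
6. Repeat the results without route-2 patients, and by registration before or after 01-March-2019.

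Steps 1 to 3 use the end-of-use reason and any end-of-use EF the registry already collects.

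**Cost.** The all-patient share becomes less favourable, and EF after early stopping is incomplete. An all-registry denominator is therefore not clean without step 4: early stoppers without recovery have no scheduled 180-day EF, and counting them all as not recovered biases the share down. The bounds are as wide as that group's share of the cohort, so 10% of patients without a later EF means bounds 10 percentage points apart. Opening study entry to all early enders would be a larger change to eligibility, consent and follow-up, and this fix does not need it.
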